## **Study Synopsis**

	· · · ·				
Study Title	Clinical evaluation of the safety and Efficacy of using Multi-Polar RF and PEMF technologies for the treatment of the Mons Pubis, Vaginal Introitus and Labia Skin Laxity				
Protocol No:	CS2815				
Device Name:	Modified Venus Versa (MP)  device with Freeze Diamondpolar and Investigational Applicators				
Design	Feasibility, single-center, baseline-controlled, prospective study				
Projected Study period	Initiation Date: February 2016 Completion Date: February 2017				
Objectives	
 
Primary objectives
 
To evaluate the safety of treating the mons pubis, labia and vaginal introitus with the Freeze Diamond Polar applicator.
 
To evaluate the safety of the internal treatment of the vagina with an investigational applicator
 
To verify the efficacy of using the Freeze Diamond Polar applicator for improving general skin appearance of the mons pubis, vaginal introitus and the labia including improvement of skin irregularities and skin laxity.
 
To determine and/or quantify any potential regenerative properties associated with the study treatments.
 
Secondary objectives
 
To evaluate subject's assessment of comfort and pain associated with treatments.
 
To evaluate subject's satisfaction with treatment results and assessment of improvement.
 
To determine if any regenerative properties are associated with the
 
				
Hypothesis	
 
Mons pubis, Vaginal Introitus and the Labia.
 
The study will confirm that the Freeze Diamondpolar applicator is safe for treating the mons pubis, labia and vaginal introitus which will result in improvement in general skin appearance including an improvement in skin irregularities and skin laxity.
 
The study will confirm that the investigational applicator is safe for
 
				
Study population	internal treatment of the vagina.  1 site with 10 subjects				
Main Inclusion Criteria	
 
Healthy female between the ages of 25 and 65.
 
Sexual activity (vaginal intercourse once per month) in a monogamous relationship.
 
Requesting aesthetic benefit to the vaginal mons, introitus and labia.
 
				

Confidential 2

Protocol: CS2815v4 Approval Number: IRCM-

Main Skin Related Exclusion Criteria  Investigational Treatment and	
 
Pregnant or intending to become pregnant during the course of study. A urine pregnancy test will be given to women of childbearing potential and performed during initial visit.
 
Having any active electrical implant anywhere in the body, such as a pacemaker or an internal defibrillator.
 
Having a permanent implant in the treated area.
 
Each subject will receive three treatments at four week intervals and return for follow-up visit at one (± seven days) month after the last
 

Study Duration	treatment for evaluation of the treated areas.
Criteria for Evaluation	
 
Number and type of any adverse events throughout the study will be recorded.
 
General skin appearance improvement at FU3 compared to baseline as assessed by independent evaluators by photographic assessment, utilizing the GAI Scale.
 
Secondary endpoints
 
Subject's assessment of pain associated with treatments using a VAS scale, following each of the 3 treatments.
 
Investigator assessment of immediate and short term response following each treatment, defined as type and intensity of response and the time it takes for it to subside.
 
Subject's satisfaction with the results and assessment of improvement in skin appearance using a GAI scale.
 
Subject's vaginal pH with results from pH paper sampling of the vaginal mucosa.
 
Subject's histologic and molecular pathology changes with standard
 

Confidential 3

#### 1.0 Introduction

#### 1.1 Rationale for Evaluation

The combination of Multi-Polar RF and PEMF technology has been shown in clinical studies to improve skin laxity, and to treat various skin conditions related to aging and alternate collagen structures such as wrinkles, rhytids, etc.

The objective of this clinical study is to evaluate the modified Venus Versa (MP) system™ clinical performance in improving the mons pubis and labia general skin appearance including skin laxity and loss of vaginal introitus coaptation (normal closure of vaginal opening) and various skin irregularities using the Freeze Diamondpolar applicator. The safety of an investigational applicator for treatment of the vagina will also be investigated.

The use of the modified Venus Versa has been determined to present non-significant risk in accordance with 21 CFR 812.3 for the intended use in this study, **because the device is not:** 

- Intended as an implant and presents a potential for serious risk to the health, safety, or welfare of a subject;
- Is purported or represented to be for use supporting or sustaining human life and presents a potential for serious risk to the health, safety, or welfare of a subject;
- Is for a use of substantial importance in diagnosing, curing, mitigating, or treating disease, or otherwise preventing impairment of human health and presents a potential for serious risk to the health, safety, or welfare of a subject; or
- Otherwise presents a potential for serious risk to the health, safety, or welfare of a subject.

Furthermore, RF technology has been used previously for the external and internal female genitalia without incident or complications, see for example Millheiser LS et al., 2010; Sekiguchi Y. et al., 2013; and Dover RR., 2002. (Use of Multi-Polar RF and PEMF technology was already demonstrated to be safe and efficient in delivering heat to the tissue (Nils Krueger et al., 2012; Dover J. et al., 2014). The study device therefore poses no clinically significant risk to the subjects or operator(s) of the device.

This study will be conducted in compliance with the protocol and according to Good Clinical Practice (GCP) standards.

### 2 Study Design

This is a single center, baseline-controlled, prospective study. Ten (10) and up to three hundred (300) subjects that meet the inclusion criteria will be enrolled from the site's pool of patients. Subjects should be female, at the age of 25-65 years, and have a suitable treatment area (e.g. skin irregularities and/or unwanted skin laxity in the mons pubis, introitus and/or labia area).

Subjects will receive three treatments with the study device and both applicators, at four week intervals, followed by one month follow-up visits after the last treatment.

Confidential 6

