## 5 Patient Population

### 5.1 Source and Sample Size

Subjects shall be recruited by the investigator from within the investigator's patient population. Subjects shall Confidential

be with skin type I-VI and have unwanted skin laxity in the mons pubis and/or labia area. Each subject (no less than 10 subjects and no more than 300 subjects) included for treatment will receive three treatments at four week intervals and return for follow-up visit at one month (± seven days) after the last treatment for evaluation of the treated areas. Enrolled subjects that did not complete the full course of the study will not be replaced.

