### 8.2 Sample Size Justification

The proposed study is a feasibility study for evaluating the safety and the efficacy of using the Freeze Diamond Polar applicator for treatment of the mons pubis, vaginal introitus and labia anatomical areas and the investigational applicator for treatment of the vagina. Based on previous experience with other RF devices, we believe that the proposed study sample of 10 subjects per each anatomical area (total of 10) will be sufficient to evaluate the safety and the efficacy of the treatment and to obtain qualitative assessments of comfort levels experienced during treatments.

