## 12.7 Appendix I – Additional Safety Background Data

Non-ablative or non-burning RF therapy has been used for vaginal tightening previously within human vaginal mucosa at 75-90 J/m2. (J Sex Med 2010 Sep; 7(9): 3088). For the purpose of this study premenopausal patients will be treated at 90J/m2, whereas the post menopausal patients will be treated with less cumulative heat. We have calculated that the thickness of vagina epithelium (the most susceptible tissue to thermal injury) is decreased 16% in menopause. (This has been calculated by the percent change seen in human vaginal epithelium of menopausal versus non-menopausal on histomorphometry measurements -J. Sex Med 2009 Nov 6(11): 3097.) Reducing energy delivery by 16% yields a safe basement level of 75.6 J/m2 for menopausal patients. Again it is important to emphasize the proposed study device has thermal feedback safety settings and real-time multipolar thermal control to virtually eliminate the possibility of tissue burns. Additionally, now over 3 patients have been treated in Geneva Switzerland with [name], using the proposed study device (Venus Versa) both internally intravaginal and externally. No burns or off target damage was appreciated.

On advisement from the IRB committee and combined with the above information update; for further patient protection we will modify the protocol to perform initial safety parameters on the first 10 patients using 75J/m2 for premenopausal patients and 90J/m2 for premenopausal patients. If these safety parameters are consistent with the preliminary safety studies in Europe, the IRB will review these results, at which time we will submit an expanded study of up to 300 for review.

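### Sections 2 and 5.1 permit 10 to 300 subjects with no hold, although Appendix I makes the first 10 a safety stage that the IRB reviews before an expansion to 300

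*Combined protocol and SAP*

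**What the plan says.** The two sections that set enrolment give a range. Section 2 states: "Ten (10) and up to three hundred (300) subjects that meet the inclusion criteria will be enrolled". Section 5.1 has "no less than 10 subjects and no more than 300 subjects". Neither divides the range into steps or refers to an IRB decision.

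Two other places give a single number. The synopsis has "1 site with 10 subjects". Section 8.2 rests its justification on "the proposed study sample of 10 subjects per each anatomical area (total of 10") and offers no reasoning for any larger number.

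Appendix I sets out a staged plan. It begins "On advisement from the IRB committee and combined with the above information update" and goes on: "for further patient protection we will modify the protocol to perform initial safety parameters on the first 10 patients". The next step is conditional: "If these safety parameters are consistent with the preliminary safety studies in Europe, the IRB will review these results". The larger number enters only after that, as a further submission: "at which time we will submit an expanded study of up to 300 for review".

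Section 8.3 plans one interim safety report, drawn from data collected just after the first treatment of everyone enrolled. The report feeds into later treatment settings. The section adds that interim reports have no influence on whether the study goes on, and that the study will be completed under the protocol whatever they show.

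**The concern.** The number 300 has two meanings in one document. In Sections 2 and 5.1 it is a ceiling already in force. In Appendix I it is something still to be submitted, after the IRB has seen results from 10 patients.

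The difference matters because the staged plan is a safeguard that the IRB asked for. Subjects receive internal treatment with an investigational applicator, and the prior internal use of the study device described in Appendix I amounts to just over 3 patients. If the sections that staff consult for enrolment do not carry the hold, it depends on someone finding it in an appendix titled as safety background. The body cites that appendix only in the risk discussion (Section 9.3.1).

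**Working it through.** The plan gives no calculation to reproduce: Section 8.2 sets 10 by judgement, with no error rate, power, effect size or event rate. The check is a comparison of the texts.

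| Place | Number of subjects | Step required before subject 11 |
|---|---|---|
| Synopsis | 10 | Not applicable |
| Section 2 | 10 to 300 | None stated |
| Section 5.1 | 10 to 300 | None stated |
| Section 8.2 | 10 | Not applicable |
| Appendix I | 10, then up to 300 | IRB review of the first 10, then submission of the expansion |

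**Which number is better supported.** The synopsis, Section 8.2 and the first stage of Appendix I agree on 10. Only Sections 2 and 5.1 present 300 as current. Those two sections are the text to correct.

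**How much lies beyond the first stage.** 300 − 10 = 290, and 290/300 = 96.7%.

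**Does another provision stop enrolment at 10?**

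- Section 10.9 requires IRB approval of medically significant amendments. Enrolling subject 11 alters no text in Section 2 or 5.1, so it does not clearly trigger that rule.
- Section 9.1.6 (ethics committee told within 10 working days of an anticipated event likely to affect safety), Section 9.2.1 (serious events to the monitor within 24 hours) and the burn procedure in Appendix I (written report to the IRB Chairman within 7 days) all require notification. None suspends enrolment.
- Section 8.3 gives the interim report no power over continuation.

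**Section 8.3 against Appendix I.** If N = 10, everyone enrolled is in the first 10. Finishing their treatment is compatible with a review that governs only the expansion. If enrolment runs past 10, the interim report is no longer tied to the first 10, and continuing regardless contradicts a decision that Appendix I leaves to the IRB.

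**Length of the implied pause.** If the review uses full follow-up, it waits for Visit 4 of the tenth subject: 3 intervals × 4 weeks = 12 weeks after her first treatment. This is approximate, because Section 7.1 gives the treatment intervals as approximate and the 7-day window applies only to the final visit.

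**Context only.** With no events in 10 subjects, the exact one-sided 95% upper limit on an event rate is 1 − 0.05^(1/10) = 25.9%. A clean first stage would still leave wide uncertainty, so expansion deserves a deliberate decision. The documents give no event rate, so no event count is projected for the other 290.

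**The case against.** The strongest reply is that the safeguard is already in the protocol. Appendix I is part of the document, completing the study under the protocol includes Appendix I, and the range in Section 2 can be read as shorthand for the two steps. With the synopsis and Section 8.2 also at 10, harm requires a site to follow two sentences and overlook three other places. This has force: it makes the defect an inconsistency of text rather than a missing safeguard, and it supports 10 as the intended number. It does not remove the defect, because the sections that set enrolment grant 300 without condition and do not point to Appendix I.

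A second reply is that the IRB may already have approved 300. The approval history is not in the documents, so this cannot be excluded. But Appendix I still puts the submission in the future and two places still say 10. If approval exists, those passages are out of date and need correcting instead.

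Three stronger readings are tempting and are not supported:

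- A reader might infer that Section 8.3 flatly contradicts Appendix I. It does so only above 10 subjects. Completing this study and approving an expanded one are separate decisions, and the interim report does affect treatment settings.
- A reader might infer from the six months in Section 7.1 that 300 was never feasible: 26 − 12 = 14 weeks to enrol, or about 21 subjects a week. The synopsis gives February 2016 to February 2017. On that period 52 − 12 = 40 weeks remain, or 300/40 = 7.5 a week. The two timelines disagree and no site capacity is stated, so the argument settles nothing.
- A reader might infer that data through Visit 2 cover only a third of the 30 planned sessions in the first 10 subjects. The flow chart places the second treatment at Visit 2, so 20 of 30 sessions would have immediate-response data and 10 would have follow-up data.

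**Conclusion.** The point stands as an internal inconsistency. Sections 2 and 5.1 permit up to 290 subjects beyond a stage at which Appendix I promises an IRB review, and nothing else in the protocol clearly holds enrolment at 10. Section 8.3 adds to the conflict only if enrolment passes 10.

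The conclusion rests on the wording alone, not on any assumed event rate. It assumes that Appendix I, written as a change still to come, states the current intention; the remaining references to 10 favour that reading. The 290 is the number the text would allow, not a forecast, and nothing in the documents shows that anyone was enrolled outside the staged plan.

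**What to change.** Make three wording changes:

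1. **Sections 2 and 5.1:** state that 10 subjects will be enrolled, and that enrolment may be extended to at most 300 only after the IRB has reviewed the safety data from the first 10 and approved the expansion. Refer to Appendix I. This matches the synopsis and Section 8.2.
2. **Section 8.3:** add one sentence saying that the statements about interim reports not influencing continuation, and about completing the study whatever they show, apply to completing treatment and follow-up of the first 10 subjects, and that enrolment stops at 10 until the IRB approves the expansion.
3. **If the IRB has already approved 300:** record that approval and bring Appendix I, the synopsis and Section 8.2 into line instead.

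Which data go to the IRB, and what counts as agreement with the European experience, are for the sponsor and the IRB to decide.

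The change needs no new data collection. Its cost is an enrolment pause that Appendix I already implies: roughly 12 weeks from the tenth subject's first treatment if full follow-up is used, less with an earlier cut-off, plus IRB review time.

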## 3 Study Objectives

## 3.1 Primary Objectives

- To evaluate the safety of treating the mons pubis, labia and vaginal introitus with the Freeze Diamondpolar applicator.
- To evaluate the safety of the internal treatment of the vagina with the investigational applicator.
- To verify the efficacy of using the Freeze Diamondpolar applicator for improving general skin appearance of the Mons pubis and Labia including improvement of skin irregularities and skin laxity of the female genitalia and introitus.
- To determine and/or quantify any potential regenerative properties associated with the study treatments.

## 3.2 Secondary Objectives

- Subject's assessment of discomfort/pain associated with treatments using a VAS scale, following each
  of the 3 treatments.
- Subject's satisfaction with the results and assessment of improvement in skin appearance using a GAI scale.
- Subject's vaginal pH with results from pH paper sampling of the vaginal mucosa.
- Subject's histologic and molecular pathology changes with standard molecular histopathology methods.

#### 4 Outcome Measures

## 4.1 Primary Effectiveness Endpoints

• General skin appearance improvement at FU3 compared to baseline as assessed by independent evaluators by photographic assessment, utilizing the GAI Scale.

## 4.2 Secondary Endpoints

- Subject's assessment of discomfort/pain associated with treatments using a VAS scale, following each of the 3 treatments.
- Subject's satisfaction with the results and assessment of improvement in skin appearance using a GAI scale.
- Subject's vaginal pH with results from pH paper sampling of the vaginal mucosa.
- Subject's histologic and molecular pathology changes with standard molecular histopathology methods.

### 4.3 Safety Endpoint

- Immediate and short term response as assessed by the investigator following treatment, defined as type and intensity of response and the time it takes for it to subside.
- Any adverse events associated with various setting(s) used during the treatment and follow-upperiod.

## 5 Patient Population

### 5.1 Source and Sample Size

Subjects shall be recruited by the investigator from within the investigator's patient population. Subjects shall Confidential

be with skin type I-VI and have unwanted skin laxity in the mons pubis and/or labia area. Each subject (no less than 10 subjects and no more than 300 subjects) included for treatment will receive three treatments at four week intervals and return for follow-up visit at one month (± seven days) after the last treatment for evaluation of the treated areas. Enrolled subjects that did not complete the full course of the study will not be replaced.

## 5.2 Eligibility

Each subject will be evaluated by the Investigator to assess her suitability for entry into this study according to the following criteria:

#### 5.2.1 Inclusion Criteria

Subjects must meet all of the following inclusion criteria to be entered into the study:

- 1. Healthy female between the ages of 25 and 65.
- 2. Able to read, understand and voluntarily provide written Informed Consent.
- 3. Able and willing to comply with the treatment/follow-up schedule and requirements.
- 4. Fitzpatrick skin type I-VI.
- 5. Sexual activity (vaginal intercourse once per month) in a monogamous relationship.
- 6. Women of child-bearing age are required to be using a reliable method of birth control at least 3 months prior to study enrollment and have a negative Urine Pregnancy test at baseline.
- 7. Women requesting aesthetic benefit to the vaginal mons, introitus and labia.

#### 5.2.2 Exclusion Criteria

Any of the following will exclude the subject from the study:

- 1. Pregnant or intending to become pregnant during the course of study. A urine pregnancy test will be given to women of childbearing potential and performed during initial visit.
- 2. Having any active electrical implant anywhere in the body, such as a pacemaker or an internal defibrillator.
- 3. Having a permanent implant in the treated area.
- 4. Prior use of retinoids in treated area within 2 weeks of initial treatment or during the course of the study.
- 5. Use of oral Isotretinoin (Accutane®) within 6 months of initial treatment or during the course of the study.
- 6. Patient on systemic corticosteroid therapy 6 months prior to and throughout the course of the study.
- 7. Prior skin treatment with laser in treated area within 6 months of initial treatment or during the course of the study.
- 8. Prior use of collagen, fat injections and /or other methods of skin augmentation (enhancement with injected or implanted material) in treated area within 4-6 weeks of initial treatment or during the course of the study. Treatment may not be performed at all over permanent dermal implants.
- 9. Prior ablative resurfacing procedure in treated area with laser or other devices within 12 months of initial treatment or during the course of the study.
- 10. Any other surgery in treated area within 12 months of initial treatment or during the course of the study.
- 11. History of keloid formation or poor wound healing in a previously injured skin area.
- 12. History of epidermal or dermal disorders (particularly if involving collagen or microvascularity).
- 13. Open laceration or abrasion of any sort on the area to be treated.
- 14. Active STD (e.g. genital Herpes Simplex, condylomata) or vaginosis; any tissue biopsy will be deferred or

Confidential 8

delayed to a later time point until the infection is resolved.

- 15. Chronic vulvar pain or vulvar dystrophy.
- 16. History of immunosuppression/immune deficiency disorders (including HIV infection or AIDS) or use of immunosuppressive medications.
- 17. Having any form of active cancer at the time of enrollment and during the course of the study.
- 18. Significant concurrent illness, such as uncontrolled diabetes i.e. any disease state that in the opinion of the Investigator would interfere with the treatment, or healing process.
- 19. Participation in a study of another device or drug within 1 month prior to study enrollment or during this study, and as per the Investigator's careful discretion, as long as not contradictory to any of the above criteria.
- 20. Tattoos in the treatment area.
- 21. Mentally incompetent, prisoner or evidence of active substance or alcohol abuse.
- 22. Having any stage 3-4 cystocele, rectocele, enterocele paravaginal defect or major pelvic organ prolapse beyond the hymenal ring.

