## 12.6 Appendix H - Treatment Evaluation: Follow-Up Visit Client's Questionnaire (version 4)

Subject Initials:	Subject ID #:	
Have you delivered vaginally?	Yes / No, if yes, how many_	
Are you sexually active (vaginal intercourse)?	Yes / No, if yes, Av. frequency?	
Question regarding the treatments:	Answers:	
Was the treatment duration tolerable for you?	Yes / No   Too long / Too short	
2. Which of the applicators was most comfortable for you?	External / Internal / Both / None/ None Applicable	
3. How would you describe any sensations you experienced during the treatment? i.e., tingling, warm, hot, burning, itching, etc.	Open answer:	
4. Did you feel intimidated by any of the devices used during the procedure (the treatment equipment / probes/ thermometer etc.)?	Open answer:	
General questions:	Answers:	
5. Did you feel uncomfortable during the procedure (type of treatment, intimacy etc.)? Were you ever alone with your gynecologist?	Yes / No / uncertain / Not applicable Please specify: Yes / No / uncertain	
6. How frequently would you be willing to have Fiore treatments?	Open answer:	
7. What feminine areas for rejuvenation and skin tightening (mons pubis/labia)?	Open answer:	
8. Have you ever experienced similar treatment/s?	Yes / No / uncertain / Not applicable If yes, please specify:	
9. Have you suffered from any of these listed conditions?	Please mark the relevant box/s:  Pelvic prolapse	
10. How long have you experienced any of the above condition/s?	Open answer:	
11.Do you feel that the quality of your sex life is negatively affected by the conditions described above?	Open answer:	
12. Would you consider receiving hormonal therapy to address the above conditions?	Yes / No / uncertain / Not applicable	
13. Have you sought a solution, on your own initiative, to address any of the condition/s described above?	Yes / No / uncertain / Not applicable	
14. Have you spoken with your friends about any of the above condition(s)?	Yes / No / uncertain / Not applicable	
15. Have you considered in the past, or would consider, appropriate surgical solultions for the above medical conditions?	Yes / No / uncertain / Not applicable	
16.In your opinion, what would be the best way to increase awareness for Fiore types of treatments (e.g. TV or radio commercials, Facebook/Internet, magazines ads, news articles, information at physician offices, etc.)	Open answer:	
17. Would you recommend this treatment to your friends?	Yes / No / uncertain / Not applicable	

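### The exclusion criteria wash out laser but not non-study, non-ablative radiofrequency on the same area, so in a study with no comparator its effect can be counted as device effect

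*Combined protocol and SAP*

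**What the plan says.** Section 2 gives the design: "This is a single center, baseline-controlled, prospective study". Each woman is compared with herself, and the primary effectiveness endpoint (section 4.1) is the independent evaluators' GAI grade of the FU3 photographs against baseline.

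Section 5.2.2, item 7, excludes "Prior skin treatment with laser in treated area within 6 months of initial treatment or during the course of the study". The neighbouring items cover other things:
- Item 8 covers injected or implanted augmentation material, "in treated area within 4-6 weeks of initial treatment or during the course of the study".
- Item 9 extends to devices other than laser, but only for ablative resurfacing.
- Item 10 covers surgery.
- Item 19 covers another device or drug, but only when received as a participant in another study.
- Item 6 covers steroids: "Patient on systemic corticosteroid therapy 6 months prior to and throughout the course of the study".

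On RF itself, section 1.1 states that "RF technology has been used previously for the external and internal female genitalia without incident or complications", and section 6.1 describes RF heating as having an established effect on laxity. Appendix H, item 8, asks "Have you ever experienced similar treatment/s" and invites the subject to specify. Appendix A schedules that questionnaire at all four visits, including Visit 1. No eligibility criterion refers to the answer.

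**The concern.** In a single-arm study, the eligibility and washout rules do much of the work that a control group would otherwise do. Here they keep out a laser course in the previous six months but let in the study's own type of energy, applied commercially to the same tissue last month or between visits.

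The exposure is plausible. Section 5.1 recruits from the investigator's own patients, and inclusion item 7 asks for women seeking aesthetic benefit at these sites. If some of them improve because of another RF course, the FU3 GAI gives that improvement to the study device. Section 8.3 plans descriptive statistics and correlations only, with nothing to identify, exclude or adjust for such subjects.

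**Working it through.** **Step 1: is the treatment excluded anywhere?** Take a woman who has non-ablative RF tightening of the labia at a commercial clinic, outside any study, four weeks before Tx1 or between Visits 2 and 3. Item 7 does not apply (not laser). Item 8 does not apply (nothing injected or implanted). Item 9 does not apply (not ablative). Item 10 does not apply (not surgery). Item 19 does not apply (not in a study). The remaining items concern pregnancy, implants, drugs, disease, infection, tattoos, capacity and prolapse. She is eligible, and may stay in the study.

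**Step 2: when does this bias the endpoint?** GAI at FU3 is graded against the subject's own baseline photograph.
- Earlier RF, effect stable at baseline: present in both photographs, so no bias.
- Earlier RF, effect still developing at baseline: the later part falls between the photographs and is credited to the device.
- RF elsewhere after baseline: its whole effect falls between the photographs and is credited to the device.

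The documents give no time course for an RF effect, so they do not show how recent is too recent.

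**Step 3: size.** The plan states no effect size, SD or prevalence of prior RF, so there is no figure to reproduce. What follows is illustration.

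Inputs: n = 10, from section 8.2 ("the proposed study sample of 10 subjects per each anatomical area (total of 10) will be sufficient"); n up to 300, from sections 2 and 5.1. Assumed: a gain of g GAI steps from the other treatment, and improved meaning a GAI score of 1 or more, since the plan sets no responder threshold.

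Shift in mean GAI with k affected subjects = k × g / n.

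| n | k | g = 1 | g = 2 |
|---|---|---|---|
| 10 | 1 | 0.1 | 0.2 |
| 10 | 2 | 0.2 | 0.4 |
| 300 | 1 | 0.003 | 0.007 |

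Shift in improved rate = (affected subjects who cross from not improved to improved) / n. With g = 1, a subject who would have scored 0 crosses to 1, and at n = 10 adds 1/10 = 10 percentage points. One who would have scored 1 or more anyway adds nothing. The range is therefore 0 to 10 points per affected subject at n = 10, and 0 to 0.33 points at n = 300.

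A larger study does not cure a fixed prevalence: if 10% are affected, that is 1 of 10 or 30 of 300, and the improved rate can shift by up to 10 points in both.

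Chance of at least one affected subject among 10 = 1 − (1 − p)^10, with p assumed:

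| p | 5% | 10% | 20% | 30% |
|---|---|---|---|---|
| Chance | 40% | 65% | 89% | 97% |

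**Step 4: wording of items 6 and 8.** Item 8 gives a range: 4 × 7 = 28 days and 6 × 7 = 42 days. For a subject injected in that 14-day band, two sites can reach opposite answers. Item 6 joins the period before and the period during the study with *and*, whereas items 4, 5 and 7 to 10 join them with *or*. Read literally, it catches only women on steroids in both periods, and the second is unknown at enrolment.

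**The case against.** The strongest reply is that own-baseline comparison already removes earlier treatment effects, that nothing shows this site's patients have had commercial RF, and that the study is a feasibility study reported descriptively. The first part stands for stable effects, and it limits the point to developing effects and treatment after baseline. The second stands too: section 1.1 cites published RF use, not exposure in this patient pool, so prevalence is unknown. The third limits the consequences, but verifying efficacy is still a primary objective, and the FU3 GAI is how it is judged.

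Safeguards exist. Appendix H item 8 is already scheduled at Visit 1, medical history is reviewed at screening, and concomitant medication is recorded at every visit. However, the questionnaire's place in the order of Visit 1 is not stated, its answer has no effect on eligibility, the medication line does not name procedures, and section 8.3 uses none of these.

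A reader might infer three stronger points that the documents do not support:
- *That hormone changes are a comparable gap.* Appendix I says the "thickness of vagina epithelium (the most susceptible tissue to thermal injury) is decreased 16% in menopause", but this compares menopausal states and is used to set energy. It says nothing about starting or stopping hormones over the roughly 12 weeks of follow-up (three intervals of four weeks). That link would have to come from outside the documents.
- *That items 6 and 8 cannot be applied.* Item 8 fails only between days 28 and 42. Item 6 has an obvious intended meaning, and item 16, which excludes immunosuppressive medication, may catch some steroid users anyway.
- *That steroid use would inflate the GAI.* No passage says that steroids improve laxity.

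**Conclusion.** The gap is real: non-study, non-ablative RF or other energy-based treatment of the treated area is permitted before and during the study, while laser is not. With no comparator and no planned handling of co-treatments, its effect can be counted as device effect in the primary GAI. It need not be, since that requires an effect still developing at baseline or treatment received after it.

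The actual bias cannot be calculated. The figure of 0.1 on the mean and 0 to 10 points on the improved rate per affected subject rests on n = 10, an assumed one-step gain and an assumed threshold for improved. This should be corrected because it touches the primary endpoint and the remedy is cheap. The wording of items 6 and 8 is a secondary, editorial matter.

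**What to change.** 1. **Item 7.** Extend it from laser to radiofrequency and other non-ablative energy-based treatments of the treated area, external or internal, before and during the study, on the same basis as laser. The sponsor should confirm the window.
2. **Appendix H, item 8.** Add date and modality. State that it is completed before Tx1 at Visit 1 and that the answer is used for eligibility. The later scheduled administrations can then show treatment received between visits.
3. **Item 8.** Replace the range with a single cut-off chosen by the sponsor.
4. **Item 6.** Reconcile its wording with the form used in the neighbouring items, so that it gives one answer at enrolment and a separate rule during the study.

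The cost is a protocol amendment to a few lines and one expanded question. The downside is a few more screen failures from the site's aesthetic patient pool.
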